# Table 10. Customised MedDRA Query (CMQ) List of Preferred Terms for Drug Related Hepatic Disorders

Acute on chronic liver failure	Liver dialysis
Acute yellow liver atrophy	Liver disorder
Ascites	Liver injury
Asterixis	Liver operation
Bacterascites	Liver transplant
Biliary cirrhosis	Lupoid hepatic cirrhosis
Biliary cirrhosis primary	Minimal hepatic encephalopathy
Biliary fibrosis	Mixed liver injury
Cholestatic liver injury	Nodular regenerative hyperplasia
Chronic hepatic failure	Non-alcoholic fatty liver
Coma hepatic	Non-alcoholic steatohepatitis
Cryptogenic cirrhosis	Non-cirrhotic portal hypertension
Diabetic hepatopathy	Oedema due to hepatic disease
Drug-induced liver injury	Oesophageal varices haemorrhage
Duodenal varices	Peripancreatic varices
Gallbladder varices	Portal fibrosis
Gastric variceal injection	Portal hypertension
Gastric variceal ligation	Portal hypertensive enteropathy
Gastric varices	Portal hypertensive gastropathy
Gastric varices haemorrhage	Portal vein cavernous transformation
Hepatectomy	Portal vein dilatation
Hepatic atrophy	Porto pulmonary hypertension
Hepatic calcification	Renal and liver transplant
Hepatic cirrhosis	Retrograde portal vein flow
Hepatic encephalopathy	Reye's syndrome
Hepatic encephalopathy prophylaxis	Reynold's syndrome
Hepatic failure	Splenic varices
Hepatic fibrosis	Splenic varices haemorrhage
Hepatic hydrothorax	Steatohepatitis
Hepatic infiltration eosinophilic	Subacute hepatic failure
Hepatic lesion	Varices oesophageal
Hepatic necrosis	Varicose veins of abdominal wall
Hepatic steato-fibrosis	Anorectal varices
Hepatic steatosis	Anorectal varices haemorrhage
Hepatitis fulminant	Intrahepatic portal hepatic venous fistula
Hepatobiliary disease	Peritoneovenous shunt
Hepatocellular foamy cell syndrome	Portal shunt
Hepatocellular injury	Portal shunt procedure
Hepatopulmonary syndrome	Small-for-size liver syndrome
Hepatorenal failure	Spider naevus
Hepatorenal syndrome	Splenorenal shunt
Hepatotoxicity	Splenorenal shunt procedure
Intestinal varices	Spontaneous intrahepatic portosystemic venous shunt
Intestinal varices haemorrhage	Stomal varices

## Table 10. Customised MedDRA Query (CMQ) List of Preferred Terms for Drug Related Hepatic Disorders

Varicose vein	
Hepatitis, non-infectious	
Acute graft versus host disease in liver	Hepatitis fulminant
Allergic hepatitis	Hepatitis toxic
Autoimmune hepatitis	Ischaemic hepatitis
Chronic graft versus host disease in liver	Lupus hepatitis
Chronic hepatitis	Non-alcoholic steatohepatitis
Graft versus host disease in liver	Radiation hepatitis
Hepatitis	Steatohepatitis
Hepatitis acute	Granulomatous liver disease
Hepatitis cholestatic	Liver sarcoidosis
Hepatitis chronic active	Portal tract inflammation
Hepatitis chronic persistent	
Liver related investigations, signs and symptoms	6
Alanine aminotransferase abnormal	Hypercholia
Alanine aminotransferase increased	Hypertransaminasaemia
Ammonia abnormal	Kayser-Fleischer ring
Ammonia increased	Liver function test abnormal
Ascites	Liver induration
Aspartate aminotransferase abnormal	Liver palpable
Aspartate aminotransferase increased	Liver scan abnormal
Bacterascites	Liver tenderness
Bile output abnormal	Mitochondrial aspartate aminotransferase increased
Bile output decreased	Molar ratio of total branched-chain amino acid to tyrosine
Biliary ascites	Oedema due to hepatic disease
Bilirubin conjugated abnormal	Perihepatic discomfort
Bilirubin conjugated increased	Retrograde portal vein flow
Bilirubin urine present	Total bile acids increased
Biopsy liver abnormal	Transaminases abnormal
Blood bilirubin abnormal	Transaminases increased
Blood bilirubin increased	Ultrasound liver abnormal
Blood bilirubin unconjugated increased	Urine bilirubin increased
Bromosulphthalein test abnormal	X-ray hepatobiliary abnormal
Child-Pugh-Turcotte score abnormal	5'nucleotidase increased
Child-Pugh-Turcotte score increased	Blood alkaline phosphatase abnormal
Computerised tomogram liver	Blood alkaline phosphatase increased
Foetor hepaticus	Blood cholinesterase abnormal
Galactose elimination capacity test abnormal	Blood cholinesterase decreased
Galactose elimination capacity test decreased	Deficiency of bile secretion
Gamma-glutamyltransferase abnormal	Glutamate dehydrogenase increased
Gamma-glutamyltransferase increased	Haemorrhagic ascites
Guanase increased	Hepatic fibrosis marker abnormal
Hepaplastin abnormal	Hepatic fibrosis marker increased
Hepaplastin decreased	Hypoalbuminaemia

# Table 10. Customised MedDRA Query (CMQ) List of Preferred Terms for Drug Related Hepatic Disorders

Hepatic artery flow decreased	Leucine aminopeptidase increased
Hepatic congestion	Liver function test decreased
Hepatic enzyme abnormal	Liver function test increased
Hepatic enzyme decreased	Liver iron concentration abnormal
Hepatic enzyme increased	Liver iron concentration increased
Hepatic function abnormal	Model for end stage liver disease score abnormal
Hepatic hydrothorax	Model for end stage liver disease score increased
Hepatic hypertrophy	Periportal oedema
Hepatic mass	Peritoneal fluid protein abnormal
Hepatic pain	Peritoneal fluid protein decreased
Hepatic sequestration	Peritoneal fluid protein increased
Hepatic vascular resistance increased	Pneumobilia
Hepatobiliary scan abnormal	Portal vein flow decreased
Hepatomegaly	Portal vein pressure increased
Hepatosplenomegaly	Retinol binding protein decreased
Hyperammonaemia	Urobilinogen urine decreased
Hyperbilirubinaemia	Urobilinogen urine increased
Hepatic disorders specifically reported as alcohol-related	
Alcoholic liver disease	Hepatic steato-fibrosis
Cirrhosis alcoholic	Hepatitis alcoholic
Fatty liver alcoholic	Zieve syndrome

# 6.7.2 Customised MedDRA Query (CMQ) List of Preferred Terms for Injection Site Reaction Table 11. Customised MedDRA Query (CMQ) List of Preferred Terms for Injection Site Reaction

Immediate post-injection reaction	Injection site ulcer
Injection related reaction	Injection site urticaria
Injection site abscess	Injection site vesicles
Injection site cellulitis	Injection site warmth
Injection site infection	Injection site ischaemia
Injection site pustule	Injection site coldness
Injection site abscess sterile	Injection site discolouration
Injection site anaesthesia	Injection site photosensitivity reaction
Injection site atrophy	Injection site swelling
Injection site bruising	Injection site discomfort
Injection site cyst	Injection site calcification
Injection site dermatitis	Injection site movement impairment
Injection site erosion	Injection site lymphadenopathy
Injection site erythema	Injection site nodule
Injection site extravasation	Embolia cutis medicamentosa
Injection site fibrosis	Injection site scar
Injection site granuloma	Injection site discharge

Table 11. Customised MedDRA Query (CMQ) List of Preferred Terms for Injection Site Reaction

Injection site haematoma	Injection site pallor
Injection site haemorrhage	Injection site papule
Injection site hypersensitivity	Injection site injury
Injection site hypertrophy	Injection site scab
Injection site induration	Injection site eczema
Injection site inflammation	Injection site streaking
Injection site irritation	Injection site dryness
Injection site mass	Injection site laceration
Injection site necrosis	Injection site macule
Injection site nerve damage	Injection site vasculitis
Injection site oedema	Injection site exfoliation
Injection site pain	Injection site dysaesthesia
Injection site paraesthesia	Injection site plaque
Injection site phlebitis	Injection site hyperaesthesia
Injection site pruritus	Injection site hypoaesthesia
Injection site rash	Injection site hypertrichosis
Injection site reaction	
Injection site thrombosis	

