5.2 Inclusion Criteria

A participant must meet **all** of the following criteria to be eligible for inclusion in this study:

- 1. Has signed the informed consent form (ICF) and is able and willing to comply with the requirements and restrictions listed therein.
- 2. Is 18 years of age or older at the time of signing the ICF.
- 3. Currently meets DSM-5 criteria for moderate or severe OUD.
- 4. Has a history of OUD as defined by documented medical history of OUD for at least 90 days immediately prior to providing informed consent.
- Meets at least 1 of these criteria for high-risk opioid use at the Screening visit:
 - a. using opioids via the injection route for an average of 5 or more days per week in the last 4 weeks.
 - b. using at least 500 mg IV heroin equivalent (e.g., 1250 mg IV morphine) or self-reported use of any dose of highly potent synthetic opioids (fentanyl and analogues excluding transdermal patches) for an average of 5 or more days per week in the last 4 weeks by any route (See Appendix 22.8, Morphine Dose Analgesic Equivalence Table).
- 6. Is seeking medication for the treatment of OUD.
- 7. Is an appropriate candidate for opioid partial-agonist MOUD in the opinion of the Investigator or medically qualified sub-Investigator.

- 8. Agrees not to use buprenorphine-containing products other than those administered as part of study treatment for the duration of the treatment period.
- 9. A female participant is eligible to participate if she is not pregnant (as confirmed by a negative serum or urine human chorionic gonadotrophin test, not lactating and, if of childbearing potential, agrees not to become pregnant while on the study and to use medically acceptable means of contraception while on the study). The following methods of contraception are considered to be medically acceptable: established use of oral, injected or implanted hormonal contraception; placement of an intrauterine device or intrauterine system; or use of a double-barrier method of contraception (condom or occlusive cap with use of a spermicide).

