9.13 Permitted Concomitant Therapies

The Investigator may prescribe concomitant medications or treatments deemed necessary to the participant, except those medications defined in Section 9.10 and Section 9.11 of this protocol.

If the participant experiences withdrawal symptoms at any time (including withdrawal after RBP-6000), he/she may be treated symptomatically (SAMHSA TIP 63 2020):

- Nausea: ondansetron or metoclopramide
- Diarrhoea: loperamide
- Anxiety, irritability, sweating: clonidine
- Insomnia: diphenhydramine, trazodone
- Pain: nonsteroidal anti-inflammatory drugs

Participants who experience opioid withdrawal after RBP-6000 administration may be treated with non-opioid medications as described above.

For rapid induction participants, if precipitated withdrawal occurs post TM buprenorphine that would prevent RBP-6000 administration, an additional 4 mg TM buprenorphine may be re-administered later that same day at the discretion of the Investigator. Alternatively, the Investigator may permit the participant to return to the

facility on another day within 30 days of informed consent. Returning participants will repeat all Day 1 scheduled assessments. In addition for rapid induction participants, adjunctive use of TM buprenorphine in increments of 2 to 4 mg up to a maximum of 12 mg may be administered on Day 1 (i.e., 12 mg total TM buprenorphine on Day 1, inclusive of pre–RBP-6000 TM buprenorphine) at the discretion of the Investigator to alleviate withdrawal symptoms after the first injection of RBP-6000.

Investigators will be asked to identify concomitant medications administered to alleviate withdrawal symptoms.

Participants will not be discontinued from treatment due to non-prescribed opioid use (including TM buprenorphine), but use should be captured on the TLFB.

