#### 5.1.4 Open-label Induction Sub-study Period

The treatment period for the OLIS begins when the first TM BUP dose is given and ends immediately prior to a participant receiving double-blind RBP-6000 Injection 3. Note that predose assessments for Injection 3 are considered part of the OLIS. See Figure 1 for the OLIS schematic.

For the RI arm, the Induction Day 1 Visit of the most recent induction attempt and the Week 1 Day 1 Visit for the first RBP-6000 injection occur on the same calendar day. In the protocol, this day is the "Day 1" of the RI arm: the RI participants receive their first RBP-6000 injection about 1 hour post TM BUP and then remain on site about 4 hours post injection. The investigator-evaluated PWs occurring within the 1-hour window post TM BUP under Induction Day 1 Visit and those occurring within the 4-hour window post RBP-6000 injection under Week 1 Day 1 Visit are recorded on "Day 1" of the RI arm.

[figure not shown]
For the SoC arm, the Week 1 Day 1 Visit for the first RBP-6000 injection occurs about 7 to 14 days after the Induction Day 1 Visit. At the Induction Day 1 Visit (of the most recent induction attempt), the SoC participants remain on site about 5 hours after the first TM BUP, to serve as the control period for the 5-hour on-site duration post TM BUP on "Day 1" of the RI arm; at Week 1 Day 1 Visit, the SoC participants remain on site about 4 hours post RBP-6000 injection at Week 1 Day 1 Visit, to serve as the control period for the 4-hr on-site duration post injection on "Day 1" of the RI arm.

Therefore, the Induction Day 1 Visit or the Week 1 Day 1 Visit will be used to refer to the "Day 1" of the RI arm, depending on which visit of the SoC arm is to be compared.

Handling of multiple Induction Check-in Days/repeat attempts at induction are described in the analysis sections for the individual endpoints. Example scenarios that may result in multiple Induction Check-in Days/repeated attempts at induction are the following:

- PW from TM BUP that would prevent RBP-6000 administration
- Participant must leave before the in-clinic assessments on an Induction Day Visit are completed

Figure 1. Open-label Induction Sub-study Schematic

BUP=buprenorphine; min=minimum; SoC=standard of care; TM=transmucosal

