#### **5.4.2.1** Definition of endpoints

These endpoints will encompass all induction attempts, and therefore utilise the first dose of TM BUP for derivations. A treatment-emergent adverse event (TEAE) is defined as an AE having an onset date/time after administration of the first TM BUP dose and before the date/time of Injection 3. The TEAEs are classified into the 2 consecutive time intervals, defined as:

• TEAEs up to RBP-6000 Injection 2 are TEAEs with a start date/time on or after the first dose of TM BUP and before the date/time of Injection 2

 TEAEs between RBP-6000 Injections 2 and 3 are TEAEs with a start date/time on or after Injection 2 and before the date/time of Injection 3

Note: If AE onset time is missing, then only the onset date will be used to assign TEAE status. An AE onset date on or after the date of the administration of the first dose of TM BUP will be considered a TEAE.

For participants who received Injections 1 and 3 (but not Injection 2), their TEAE with start date before the date of Injection 3 will be classified into the time interval of "up to RBP-6000 Injection 2". For discontinued participants whose last injection was Injection 1, their TEAE with start date after the last injection will be classified into the time interval of "up to RBP-6000 Injection 2". For discontinued participants whose last injection was Injection 2, their TEAE with start date after the last injection will be classified into the time interval of "between RBP-6000 Injections 2 and 3".

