### 5.4.2.2 Main analytical approach

The number and proportion of participants with at least 1 TEAE, treatment-related TEAE, serious TEAE, fatal TEAE, serious TEAE meeting LFT criteria, severe TEAE, TEAE leading to discontinuation, or TEAE reported as adverse events of special interest, drug-related hepatic disorders (see definition in Section 6.7.1), injection site reactions (see definition in Section 6.7.2), opioid withdrawal symptoms, and precipitated withdrawal symptoms (per eCRF) will be summarised for each endpoint, by induction arm within randomisation strata and for overall.

The numerator of the proportion for each endpoint will be the number of participants with at least 1 TEAE of interest in the respective time interval. The denominator for endpoint 2 (TEAEs up to RBP-6000 Injection 2) will be the number of participants in the SFAS population. The denominator for endpoint 3 (TEAEs between RBP-6000 Injections 2 and 3) will be the number of the participants in the SFAS population who received Injection 2.

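### The injection-site-reaction summaries count listed terms from the first transmucosal buprenorphine dose, with no condition that RBP-6000 had been injected

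*SAP*

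**What the plan says.** SAP 5.4.2.2 lists, among the event categories for secondary endpoints 2 and 3, "injection site reactions (see definition in Section 6.7.2". That section is Table 11, titled "Customised MedDRA Query (CMQ) List of Preferred Terms for Injection Site Reaction", and it contains preferred terms only. It sets no condition on timing, body site or product. SAP 5.6.2 applies the same query to the general adverse event tables.

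The events to which the query is applied come from SAP 5.4.2.1. A treatment-emergent event there is "an AE having an onset date/time after administration of the first TM BUP dose and before the date/time of Injection 3". The first interval is defined by "TEAEs up to RBP-6000 Injection 2 are TEAEs with a start date/time on or after the first dose of TM BUP". On repeat inductions the section says: "These endpoints will encompass all induction attempts, and therefore utilise the first dose of TM BUP for derivations".

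SAP Table 5 admits a participant to the SFAS on TM buprenorphine, without requiring an RBP-6000 injection. SAP 5.4.2.2 uses the whole SFAS as the denominator for endpoint 2, but limits endpoint 3 to participants who received Injection 2.

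The arms differ in when RBP-6000 starts. SAP 5.1.4 says of SoC induction that "the Week 1 Day 1 Visit for the first RBP-6000 injection occurs about 7 to 14 days after the Induction Day 1 Visit", whereas rapid-induction participants are injected about one hour after TM buprenorphine.

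SAP 5.6.2 also plans two relevant tables: SoC events before Injection 1 (the Run-in Period), and events related to RBP-6000. Both are by system organ class and preferred term.

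**The concern.** The secondary objective of the sub-study is the safety and tolerability of RBP-6000. Protocol 1.3.1 names injection site reactions as the expected departure from the TM buprenorphine safety profile, so a reader will take this row as local tolerability of RBP-6000. An event that starts before any RBP-6000 injection cannot be that.

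The population makes the gap more than a formality. One route to eligibility is "using opioids via the injection route for an average of 5 or more days per week in the last 4 weeks", and Protocol 9.13 states: "Participants will not be discontinued from treatment due to non-prescribed opioid use". Protocol section 10 treats an untoward medical occurrence as an adverse event whether or not it is causally related. Table 11 includes abscess, cellulitis, infection, phlebitis and thrombosis at an injection site. A complication at a non-study injection site could therefore reach the query, before or after Injection 1.

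At stake is the meaning of one safety row that is shown by induction arm, where the arms spend very different amounts of time under observation before RBP-6000.

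**Working it through.** The plan gives no figure for this point, so there is none to reproduce. The check traces the definitions and computes how much of the first interval precedes RBP-6000.

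**Scope of the query.** Table 11 holds 68 distinct terms. Of these, 65 begin with the words injection site; the other three are immediate post-injection reaction, injection related reaction and embolia cutis medicamentosa. None carries a timing, site or product condition, and neither 5.4.2.2 nor 5.6.2 adds one.

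**Inputs.**
- SoC run-in before Injection 1: about 7 to 14 days (SAP 5.1.4).
- Injection 1 to Injection 2: 7 to 11 days (Protocol 4.1.3, one week with a window of +4 days).
- Rapid induction, single attempt: about 1 hour before Injection 1 (SAP 5.1.4).

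**SoC arm.** Share before RBP-6000 = run-in / (run-in + Injection 1-to-2 interval), for a participant who receives both injections within these windows.

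| Run-in (days) | Injection 1 to 2 (days) | Whole interval (days) | Share before RBP-6000 |
|---|---|---|---|
| 7 | 7 | 14 | 7/14 = 50% |
| 7 | 11 | 18 | 7/18 = 39% |
| 14 | 7 | 21 | 14/21 = 67% |
| 14 | 11 | 25 | 14/25 = 56% |

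The range is 39% to 67%.

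**Rapid induction.** With one attempt the share is (1/24)/11 = 0.4% to (1/24)/7 = 0.6%. It is longer when induction is repeated, because the interval still starts at the first TM buprenorphine dose of the first attempt.

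**Numerator.** Suppose listed events unrelated to RBP-6000 arise at the same daily rate r in both arms. SoC then expects r × (14 to 25 days) and single-attempt rapid induction about r × (7 to 11 days). For the same Injection 1-to-2 interval, the SoC excess is r × (7 to 14 days), which is the run-in. The documents give no value for r, so the number of events cannot be computed.

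**Denominator.** Never-injected SFAS members cannot have a reaction to RBP-6000 but are counted in the endpoint 2 denominator. SAP section 3 reports that about 65.7% or 72.1% of those starting SoC induction in two previous studies received Injection 2. If the same held here, the never-injected share in SoC would be at most 1 − 0.657 = 34.3% or 1 − 0.721 = 27.9%. It would be smaller to the extent that losses came after Injection 1. A true reaction rate among injected participants could thus be multiplied by a factor between 0.657 and 1. This works against the numerator effect.

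**After an onset filter.** The SoC interval at risk falls from 14 to 25 days to 7 to 11 days, and the single-attempt rapid-induction interval stays at about 7 to 11 days. Endpoint 3 does not change, since every event in it starts on or after Injection 2.

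**The case against.** The strongest reply has four parts.

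- **Coding is not settled.** A non-study-site event enters the row only if it is recorded as an adverse event and coded to a listed term. SAP 5.1.1 leaves coding details to the Data Management Plan, and SAP section 1 leaves table specifications to a separate document. Protocol 8.7.2 evaluates the RBP-6000 site, and the SoC induction schedule places that evaluation only after Injection 1. This stands. A reader might infer that complications of illicit injecting will be reported as RBP-6000 reactions; the documents support only that they would be if so recorded and coded.
- **Other tables show these events.** The Run-in table and the RBP-6000-related table would display many of them, and the query output is itself by preferred term. This stands in part. The Run-in table covers SoC only and does not alter the count. Nor can it reliably be subtracted, because one participant may have listed events both before and after Injection 1. The relatedness table is not applied to the query.
- **The arm difference is mostly window length.** At an equal daily rate the SoC excess is the run-in and nothing more. This stands. What remains apart from window length is the meaning of the row: events before any RBP-6000 are labelled as injection site reactions.
- **Counting regardless of causality is conservative and the output is descriptive.** This also stands, and it argues against a causality filter. It does not argue against requiring that an injection had been given.

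**Conclusion.** The definition needs correcting. As written, a Table 11 event before any RBP-6000 injection, or in a participant who never receives one, counts as an injection site reaction if it is recorded and coded to a listed term. About 39% to 67% of the SoC interval up to Injection 2 is open to this, against about one hour for a single-attempt rapid induction. Those figures rest on the run-in and dosing windows stated in the documents and on participants who receive both injections within them.

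A reader might go further and infer that the rule makes rapid induction look locally better tolerated. The documents do not support that. Extra run-in events would raise the SoC rate, while never-injected participants in the denominator would lower it, and repeat inductions lengthen the period before RBP-6000 in the rapid arm. The net direction is uncertain. Any count of affected participants would rest on an assumed event rate, since the documents contain none.

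The effect is confined to a descriptive safety summary. The primary retention analysis does not use these events.

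**What to change.** In SAP 5.4.2.2, 5.6.2 and 6.7.2:

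1. For the injection-site-reaction rows, count a Table 11 event only if its onset is on or after RBP-6000 Injection 1.
2. Use SFAS participants who received at least one RBP-6000 injection as the denominator. Section 5.4.2.2 already takes this approach for endpoint 3.
3. Show Table 11 events with earlier onset, or in participants never injected, on a separate line.
4. Add a row for the subset recorded as related to RBP-6000, so that events attributed to non-study injection sites can be seen.

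Relatedness should not be a condition for counting. The comparison is open label, and Protocol 10.5 sets a strict standard for calling an event related, so such a filter could remove genuine reactions from the main row.

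One detail needs a sentence. SAP 6.4 can impute a missing or partial onset date to the first dose of study medication, which in the SoC arm could place the event before Injection 1. The SAP should say on which line such events appear.

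The cost is one extra filter, one extra denominator and an added row or two. Onset, injection dates and RBP-6000 relatedness are already used elsewhere in the SAP, so no new data are needed.
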